9.3. Variables

Exposure

- **Phase I of the study:** PAC (UFH [Anatomical Therapeutic Chemical [ATC] code: B01AB01], LMWH [B01AB04, B01AB05, B01AB06, B01AB12]), VKA (warfarin [B01AA03]), NOACs (apixaban [B01AF02], rivaroxaban [B01AF01], edoxaban [B01AF03], dabigatran [B01AE07])
- **Phase II of the study:** Apixaban (B01AF02), Rivaroxaban (B01AF01), Edoxaban (B01AF03), Dabigatran (B01AE07), Warfarin (B01AA03)

Outcome(s)

- **Phase I of the study**

- Sociodemographic and clinical characteristics of patients with VTE who initiated anticoagulants.
- Utilization of different anticoagulants at treatment initiation. Patients will be classified based on their index anticoagulant treatment received within 30 days after being diagnosed with VTE.
- Treatment interruption from the index anticoagulant treatment, which will be defined as when a patient has a gap with no new treatment within 30 days of the estimated end of supply, but subsequently restarts the index treatment after this period.[21] The time to treatment interruption will be defined as the period from the index date to the date of treatment interruption.
- Treatment switching will be defined as a prescription of another anticoagulant therapy that is started after the treatment initiation of the index anticoagulant treatment and within 30 days after the estimated end of supply of the index anticoagulant drug (exposure to the new anticoagulant treatment must last for at least 30 days to be considered as a treatment switch). The time to treatment switch will be defined as the period from the index date to the date of treatment switch.

Exemption: As heparin can be initiated at acute stage of DVT/PE before clinical decision to use OAC, a switch from initial heparin treatment to an OAC within 2 weeks after heparin treatment initiation will not be considered a treatment switch.

- Treatment discontinuation (complete discontinuation; no reinitiation) will be defined as when a patient who ended their first continuous treatment episode with the index anticoagulant treatment without switching, and subsequently have no further prescriptions for that respective anticoagulant treatment during all available follow-up time. The time to treatment discontinuation will be defined as the period from the index date to the date of treatment discontinuation.
- Overall anticoagulant treatment duration will be defined as the time period from the index date to the earliest of treatment interruption, switch, or discontinuation.
- If a patient has evidence of a repeat prescription within 30 days of the end of their prescription and does not experience any of the above events (treatment interruption, switch, or discontinuation), they will be assumed to be persistent on treatment.[21]
- Clinical event preceding first treatment change will be defined as occurrence of any event listed below within 30 days before treatment interruption, switch, or discontinuation. A new clinical event will be considered 'new' when it occurs for the first time within a 6-month period for acute conditions (arterial

thromboembolism, ischemic stroke, transient ischemic attack, myocardial infarction, angina pectoris, acute kidney injury, and abnormal liver function) and 5-years for chronic conditions (cancer, chronic kidney disease, and liver disease). A patient may contribute to multiple events.

- ① Major bleeding (as defined in Table 2)
- ② Complications of VTE: post-thrombotic syndrome and chronic thromboembolic pulmonary hypertension
- ③ Thromboembolism: PE diagnosis in patients with index event as DVT only, new diagnosis of arterial thromboembolism, ischemic stroke, transient ischemic attack, myocardial infarction, or angina pectoris
- ④ Major surgery: orthopedic surgeries (knee arthroplasty, hip arthroplasty, and hip fracture surgery), cancer surgeries (stomach, colorectal, hepatobiliary, pancreatic, breast, ovarian, cervical, renal, bladder, prostate, lung, and esophageal cancers, and brain tumors), and benign surgeries (myomectomy, oophorectomy, and transurethral resection of the prostate)
- ⑤ Cancer-related event (among non-active cancer patients only): new diagnosis of active cancer
- ⑥ Kidney function change: new diagnosis of chronic kidney disease or acute kidney injury
- ⑦ Liver function change: new diagnosis of liver disease or abnormal liver function

- **Phase II of the study**

- Major bleeding will be defined using primary or secondary diagnosis codes according to the ICD-10 diagnostic codes shown in Table 2 and classified by site (intracranial, gastrointestinal [GI], and other sites) [22].

Table 2. Definition of major bleeding by site

Major bleeding	ICD-10 diagnosis code	Diagnostic definition
Intracranial hemorrhage	I60, I61, I62, I690, I691, I692, S064, S065, S066, S068	Diagnosis code + admission code + brain CT or MRI code *Brain CT or MRI: CT: HA441, HA451, HA461, HA471, HA851

		MRI: HE101, HE102, HE135, HE201, HE202, HE235, HE301, HE302, HE401, HE402, HE501, HE502, HE535
GI bleeding	I850, I983, K2211, K226, K228, K250, K252, K254, K256, K260, K262, K264, K266, K270, K272, K274, K276, K280, K282, K284, K286, K290, K3181, K5521, K625, K920, K921, K922	Diagnosis code + admission code
Other bleeding	D62, H448, H3572, H356, H313, H210, H113, H052, H470, H431, I312, N020-N029, N421, N831, N857, N920, N923, N930, N938, N939, M250, R233, R040, R041, R042, R048, R049, T792, T810, N950, R310, R311, R318, R58, T455, Y442, D683	Diagnosis code + admission code

- The earliest date of diagnosis of the major bleeding event after the index date will be defined as the outcome occurrence date.
- Patients will be followed up from the index date to the occurrence of an outcome, treatment discontinuation (30-day grace period), switch to another anticoagulants, in-hospital death, or end of the study period (31 Dec 2019) whichever comes first.

Potential Confounder(s)

- Sociodemographic characteristics such as age, sex, and index year will be assessed at the index date.
- CCI [23] and HAS-BLED [24] scores will be measured within the 6-month period prior to the index date.
- Initial presentation of VTE
 - DVT (I80.2, I80.3)
 - PE (I26.0, I26.9)
 - Both DVT and PE
- Comorbidities (ICD-10 diagnostic code) will be measured within the 6-month period prior to the index date.

- Antiphospholipid syndrome (D68.6, I82.9): As diagnosis of antiphospholipid syndrome is usually made after VTE diagnosis with subsequent diagnostic procedures, its presence will be evaluated within the 6-month period after the index date.
 - Asthma (J45)
 - Cancer (C00-C97): History of cancer (non-active) will be evaluated within a lifetime prior to the index date.
 - Chronic obstructive pulmonary disease (COPD; J40-J44)
 - Chronic kidney disease (N18, N19)
 - Chronic liver disease (B18, B19, K70-K77)
 - Diabetes mellitus (E10-E14)
 - Fracture (S22, S32, S42, S52, S62, S72, S82, S92, T10, T12)
 - Heart failure (I50)
 - Hyperlipidemia (E78)
 - Hypertension (I10-I15)
 - Ischemic heart disease (I24, I25)
 - Myocardial infarction (I21)
 - Stroke (I60-I64, I69, G45)
 - Trauma (T79, T98, V01–V99, W11–W17, W50–W52, W64, X34–X39, Y01–Y04, Y30–Y32)
- Previous use of medications (WHO-ATC code) will be measured within the 6-month period prior to the index date.
- Corticosteroids (H02)
 - Nonsteroidal anti-inflammatory drugs (NSAIDs; M01A)
 - Angiotensin-converting enzyme (ACE) inhibitors (C09A, C09B)
 - Angiotensin II receptor blockers (ARBs; C09C, C09D)

- Antiplatelet agents (aspirin [N02BA01], aspirin/dipyridamole [B01AC30], abciximab [B01AC13], beraprost [B01AC19], cilostazol [B01AC23], clopidogrel [B01AC04], iloprost [B01AC11], indobufen [B01AC10], limaprost [C04AX], ozagrel [R03DX], prasugrel [B01AC22], sarpogrelate [B01AC], ticagrelor [B01AC24], ticlopidine [B01AC05], tirofiban [B01AC17], Treprostinil [B01AC21], triflusal [B01AC18])
 - Azole antifungal agents (fluconazole [J02AC01], itraconazole [J02AC02], voriconazole [J02AC03], posaconazole [J02AC04])
 - β -blockers (C07)
 - Calcium-channel blockers (C08)
 - Selective serotonin reuptake inhibitors (SSRIs; N06AB)
 - Proton pump inhibitors (PPIs; A02BC)
 - Diuretics (C03)
 - Thiazides (C03A)
 - Vasodilators (C01D, C04A)
 - Estrogens (G03C)
 - Cyclooxygenase (COX)-2 inhibitors (M01AH)
- Number of outpatient visits within the 6-month period prior to the index date.

9.4. Data sources

We will use the nationwide HIRA database of South Korea between 1 Mar 2012 and 31 Dec 2019 to identify all variables (exposure, outcome, covariates) needed to conduct this study. The HIRA database includes healthcare utilization information of residents of South Korea, with patient identifiers anonymized. Information on age, sex, diagnosis (ICD-10 diagnostic code, date of diagnosis, setting of diagnosis [inpatient, outpatient, emergency department, and others], medications dispensed/prescribed (national drug chemical code based on the active ingredient, date of prescription, days' supply, dose, route of administration, and others). Previous validation study that compared diagnosis codes recorded in the HIRA to those of recorded in electronic medical records found an overall positive predictive value (PPV) of 82.3%.

9.5. Study size

Phase I of the study (descriptive)

Not applicable as there are no specified *a priori* hypotheses

Phase II of the study (comparative)

- The estimated number of incident patients with VTE and no history of active cancer from the 2018 HIRA-National Patient Sample (HIRA-NPS) database is 1,465, where the HIRA-NPS database is a 3% random sample of the entire Korean population of 50 million. Based on this estimation, the projected number of patients with VTE from the entire Korean population (HIRA database) of 2018 is 48,828 (1,465 * 33.33).

- Excluding period for patients with previous OAC treatment, VTE history or a history of active cancer was set to prior 3 months because HIRA NPS database used in sample size estimation was constituted of one-year data only.

1) Apixaban vs. warfarin

- Among the above-mentioned number of incident patients with VTE and no history of active cancer, those who newly initiated apixaban or warfarin was estimated to be 211 patients (14.4%; 211/1,465), where patients had no prescription for OACs and no history of VTE within the 3-month period prior to VTE diagnosis. From these 211 patients, there were 83 (39.3%) apixaban users and 128 (60.7%) warfarin users (based on 2018 HIRA-NPS data). Hence, the projected number of patients with VTE who newly initiated OACs to be present in the HIRA database in a single year is 7,032 patients (apixaban 2,766; warfarin 4,266). As this study aims to utilize data from 2013 to 2019 (7 years), the final projected number of patients with VTE who newly initiated apixaban or warfarin from the HIRA database is 49,224 patients (apixaban 19,362; warfarin 29,862).
- Considering a 95% for a two-sided CI level (α -error=0.05) and 80% power, the sample size for the comparative safety study for major bleeding events was calculated based on the following components:
 - HR for major bleeding events from previous literature: 0.31-0.75
 - Overall probability of major bleeding events from previous literature: 1.19%
 - Proportion of apixaban users among patients with VTE from the 2018 HIRA-NPS database: 39.3% (83 apixaban users; 128 warfarin users).
 - 2,013 patients with VTE treated with apixaban or warfarin are required to detect at 5% α -error, and 80% statistical power, and HR of 0.31 by sample size calculations for survival analysis; alternatively (more conservative estimate),

PFIZER CONFIDENTIAL

33,340 patients with VTE treated with apixaban or warfarin are required to detect at 5% α -error, and 80% statistical power, and HR of 0.75 by sample size calculations for survival analysis.

- As this study is expected to include 49,224 patients with VTE, with 19,362 patients treated with apixaban from the nationwide HIRA database, this study will have enough statistical power to test the hypothesis of the association between apixaban use and risk of bleeding events among patients with VTE.

2) Rivaroxaban vs. warfarin

- Among the above-mentioned number of incident patients with VTE and no history of active cancer, those who newly initiated rivaroxaban or warfarin was estimated to be 382 patients (26.1%; 382/1,465), where patients had no prescription for OACs and no history of VTE within the 3-month period prior to VTE diagnosis. From these 382 patients, there were 264 (69.1%) rivaroxaban users and 118 (30.9%) warfarin users (based on 2018 HIRA-NPS data). Hence, the projected number of patients with VTE who newly initiated OACs to be present in the HIRA database in a single year is 12,732 patients (rivaroxaban 8,799; warfarin 3,933). As this study aims to utilize data from 2013 to 2019 (7 years), the final projected number of patients with VTE who newly initiated rivaroxaban or warfarin from the HIRA database is 89,124 patients (rivaroxaban 61,593; warfarin 27,531).
- Considering a 95% for a two-sided CI level (α -error=0.05) and 80% power, the sample size for the comparative safety study for major bleeding events was calculated based on the following components:
 - HR for major bleeding events from previous literature: 0.77-1.19
 - Overall probability of major bleeding events from previous literature: 8.1%
 - Proportion of rivaroxaban users among patients with VTE from the 2018 HIRA-NPS database: 69.1% (264 rivaroxaban users; 118 warfarin users).
 - 6,630 patients with VTE treated with rivaroxaban or warfarin are required to detect at 5% α -error, and 80% statistical power, and HR of 0.77 by sample size calculations for survival analysis; alternatively (more conservative estimate), 14,967 patients with VTE treated with rivaroxaban or warfarin are required to detect at 5% α -error, and 80% statistical power, and HR of 1.19 by sample size calculations for survival analysis.
- As this study is expected to include 89,124 patients with VTE, with 61,593 patients treated with rivaroxaban from the nationwide HIRA database, this study will have enough statistical power to test the hypothesis of the association between rivaroxaban use and risk of bleeding events among patients with VTE.

3) Edoxaban vs. warfarin

- Among the above-mentioned number of incident patients with VTE and no history of active cancer, those who newly initiated edoxaban or warfarin was estimated to be 184 patients (12.6%; 184/1,465), where patients had no prescription for OACs and no history of VTE within the 3-month period prior to VTE diagnosis. From these 184 patients, there were 57 (31.0%) edoxaban users and 127 (69.0%) warfarin users (based on 2018 HIRA-NPS data). Hence, the projected number of patients with VTE who newly initiated OACs to be present in the HIRA database in a single year is 6,132 patients (edoxaban 1,900; warfarin 4,232). As this study aims to utilize data from 2013 to 2019 (7 years), the final projected number of patients with VTE who newly initiated edoxaban or warfarin from the HIRA database is 42,924 patients (edoxaban 13,300; warfarin 29,624).
- Considering a 95% for a two-sided CI level (α -error=0.05) and 80% power, the sample size for the comparative safety study for major bleeding events was calculated based on the following components:
 - HR for major bleeding events from previous literature: 0.56-0.81
 - Overall probability of major bleeding events from previous literature: 8.5%
 - Proportion of edoxaban users among patients with VTE from the 2018 HIRA-NPS database: 31.0% (57 edoxaban users; 127 warfarin users).
 - 1,282 patients with VTE treated with edoxaban or warfarin are required to detect at 5% α -error, and 80% statistical power, and HR of 0.56 by sample size calculations for survival analysis; alternatively (more conservative estimate), 9,703 patients with VTE treated with edoxaban or warfarin are required to detect at 5% α -error, and 80% statistical power, and HR of 0.81 by sample size calculations for survival analysis.
 - As this study is expected to include 42,924 patients with VTE, with 13,300 patients treated with edoxaban from the nationwide HIRA database, this study will have enough statistical power to test the hypothesis of the association between edoxaban use and risk of bleeding events among patients with VTE.

4) Dabigatran vs. warfarin

- Among the above-mentioned number of incident patients with VTE and no history of active cancer, those who newly initiated dabigatran or warfarin was estimated to be 155 patients (10.6%; 155/1,465), where patients had no prescription for OACs and no history of VTE within the 3-month period prior to VTE diagnosis. From these 155 patients, there were 26 (16.8%) dabigatran users and 129 (83.2%) warfarin users (based on 2018 HIRA-NPS data). Hence, the projected number of patients with VTE

who newly initiated OACs to be present in the HIRA database in a single year is 5,166 patients (dabigatran 866; warfarin 4,299). As this study aims to utilize data from 2013 to 2019 (7 years), the final projected number of patients with VTE who newly initiated dabigatran or warfarin from the HIRA database is 36,162 patients (dabigatran 6,062; warfarin 30,093).

- Considering a 95% for a two-sided CI level (α -error=0.05) and 80% power, the sample size for the comparative safety study for major bleeding events was calculated based on the following components:
 - HR for major bleeding events from previous literature: 0.52-0.69
 - Overall probability of major bleeding events from previous literature: 1.4%
 - Proportion of dabigatran users among patients with VTE from the 2018 HIRA-NPS database: 16.8% (26 dabigatran users; 129 warfarin users).
 - 9,361 patients with VTE treated with dabigatran or warfarin are required to detect at 5% α -error, and 80% statistical power, and HR of 0.52 by sample size calculations for survival analysis; alternatively (more conservative estimate), 29,071 patients with VTE treated with edoxaban or warfarin are required to detect at 5% α -error, and 80% statistical power, and HR of 0.69 by sample size calculations for survival analysis.
 - As this study is expected to include 36,162 patients with VTE, with 6,062 patients treated with dabigatran from the nationwide HIRA database, this study will have enough statistical power to test the hypothesis of the association between dabigatran use and risk of bleeding events among patients with VTE.

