Note: ACE, angiotensin-converting enzyme; aSD, absolute standardized difference; CCI, Charlson comorbidity index; COPD, chronic obstructive pulmonary disease; IQR, interquartile range; NSAIDs, nonsteroidal anti-inflammatory drugs; PAC, parenteral anticoagulants; SSRI, selective serotonin reuptake inhibitors; std, standard deviation

Table 16. Pre- and post-weighted baseline characteristics of patients with venous thromboembolism who newly initiated dabigatran and warfarin.

Characteristics	Pre-weighted			Post-weighted		
	Dabigatran N= (%)	Warfarin- based therapy N= (%)	aSD	Dabigatran N= (%)	Warfarin- based therapy N= (%)	aSD
Follow-up (days; median, IQR)						
Age (years; mean±std)						
Age group (years; n, %)						
18-40						
40-65						
≥65						
Sex (n, %)						
Male						
Female						
Health insurance type (n, %)						
National health insurance						
Medical aid						
Index year (n, %)						
2012						
2013						
2014						
2015						
2016						
2017						
2018						
2019						
CCI score (mean±std)						
HAS-BLED score (mean±std)						
Comorbidities (n, %)						
Antiphospholipid syndrome						
Asthma						
History of cancer						
COPD						
Chronic kidney disease						
Chronic liver disease						
Diabetes mellitus						

Fracture
Heart failure
Hyperlipidemia
Hypertension
Ischemic heart disease
Myocardial infarction
Stroke
Trauma
Previous use of
medications (n, %)
Corticosteroids
NSAIDs
ACE inhibitors
Angiotensin II
receptor blockers
Aspirin
β-blockers
Calcium-channel
blockers
SSRI
Proton pump
inhibitors
Diuretics
Thiazides
Vasodilators
Estrogens
Cyclooxygenase-2
inhibitors
Outpatient visits
(mean±std)

Note: ACE, angiotensin-converting enzyme; aSD, absolute standardized difference; CCI, Charlson comorbidity index; COPD, chronic obstructive pulmonary disease; IQR, interquartile range; NSAIDs, nonsteroidal anti-inflammatory drugs; PAC, parenteral anticoagulants; SSRI, selective serotonin reuptake inhibitors; std, standard deviation

Table 17. Risk of major bleeding events in patients with venous thromboembolism who newly initiated oral anticoagulants associated with NOAC use versus warfarin

	No of Patients	No of Events	Person-years	Incidence rate* (95% CI)	Crude HR (95% CI)	IPT-Weighted HR (95% CI)
Warfarin-based						Reference (1.00)
Apixaban						
Rivaroxaban						
Edoxaban						
Dabigatran						

Note: CI, confidence interval; HR, hazard ratio; IPT, inverse probability of treatment.

*Events per 1000 person years.

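### Study-size inputs conflict: four major-bleeding probabilities (1.19% to 8.5%) for one outcome and essentially one warfarin group, and 7 accrual years counted instead of 6.33, so adequate power is not established, chiefly for edoxaban at HR 0.81

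*Protocol*

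**What the plan says.** Protocol 9.5 gives each comparison its own event probability, attributed to earlier literature with no source beside it:

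- apixaban: "Overall probability of major bleeding events from previous literature: 1.19" per cent
- rivaroxaban: "Overall probability of major bleeding events from previous literature: 8.1" per cent
- edoxaban: "Overall probability of major bleeding events from previous literature: 8.5" per cent
- dabigatran: "Overall probability of major bleeding events from previous literature: 1.4" per cent

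The outcome is the same in all four: major bleeding by the Table 2 codes (Protocol 9.3). The comparator is new warfarin users from the 2018 patient sample, numbering 128, 118, 127 and 129. SAP Table 17 ("Risk of major bleeding events in patients with venous thromboembolism who newly initiated oral anticoagulants associated with NOAC use versus warfarin") has a single warfarin reference row for the four NOACs.

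One-year counts are scaled up with the reasoning "As this study aims to utilize data from 2013 to 2019 (7 years"). Protocol 9.1 and 9.2.1 restrict the VTE diagnosis to 1 Mar 2013 through 30 Jun 2019.

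For edoxaban at HR 0.81 the section states that "9,703 patients with VTE treated with edoxaban or warfarin are required to detect" the effect, and concludes that "this study will have enough statistical power to test the hypothesis of the association between edoxaban use and risk of bleeding events". The other three comparisons close with the same conclusion. SAP 9 repeats all of this.

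**The concern.** One warfarin group, followed under one rule for one coded outcome, has one bleeding risk. Differences in hazard ratio and allocation can move the overall probability a little between comparisons, but not by a factor of about seven. If the four literature values come from studies with different follow-up or bleeding definitions, at most one level can suit the Table 2 outcome.

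The edoxaban conclusion depends most on this choice, because its conservative hazard ratio is close to 1 and its required N rests on the highest of the four probabilities. An unsupported power claim could later lead a null edoxaban result to be read as evidence of no difference. The accrual multiplier adds a smaller error, in the same optimistic direction, to every comparison.

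**Working it through.** **Inputs.** Two-sided alpha 0.05, 80% power, hazard ratios, overall probabilities, NOAC share p and one-year totals are from Protocol 9.5. The entry window is from 9.1 and 9.2.1.

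**1. Reproduce the plan.** Schoenfeld: events = (1.96 + 0.8416)² / [p(1−p)(ln HR)²]; N = events / overall probability. For edoxaban at HR 0.81: 7.849 / (0.31 × 0.69 × 0.0444) = 826 events; 826.4 / 0.085 = 9,722, against 9,703 stated. The other conservative cases, from unrounded events (computed / stated), are apixaban 33,408 / 33,340, rivaroxaban 14,998 / 14,967 and dabigatran 29,131 / 29,071. The four stronger-HR values also agree within about 0.2%. The formula is not at fault.

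**2. Implied warfarin risk.** w = overall / [(1−p) + p × HR].

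| Comparison | Conservative HR | Stronger HR |
|---|---|---|
| Apixaban | 0.0119/0.902 = 1.32% | 1.63% |
| Rivaroxaban | 0.081/1.131 = 7.16% | 9.63% |
| Edoxaban | 0.085/0.941 = 9.03% | 9.84% |
| Dabigatran | 0.014/0.948 = 1.48% | 1.52% |

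**3. Accrual.** 1 Mar 2013 to 30 Jun 2019 is 76 months; 76/12 = 6.33 years; 7/6.33 = 1.105. The one-year totals × 76/12 become 7,032 → 44,536 (apixaban), 12,732 → 80,636 (rivaroxaban), 6,132 → 38,836 (edoxaban) and 5,166 → 32,718 (dabigatran).

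**4. Power with one common warfarin risk.** Overall = w × [(1−p) + p × HR]; power = Φ(√(N × overall × p(1−p)) × |ln HR| − 1.96). For edoxaban at w = 1.32%: overall 1.24%, about 482 events, √(482 × 0.2139) × 0.2107 − 1.96 = 0.18, so power is 57%. All rows below use the conservative HR.

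| Comparison | 6.33 y, own probability | 6.33 y, w = 1.32% | 6.33 y, w = 1.48% | 7-year N, same two risks | Required N at w = 1.48% to 1.32% |
|---|---|---|---|---|---|
| Apixaban, 0.75 | 90% | 90% | 93% | 92.5–95% | about 29,850–33,400 |
| Rivaroxaban, 1.19 | >99% | 79.6% | 84% | 83–87% | about 72,700–81,400 |
| Edoxaban, 0.81 | >99% | 57% | 62% | 61–66% | about 59,500–66,500 |
| Dabigatran, 0.69 | 84% | 80% | 84% | 84–88% | about 29,100–32,600 |

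At w = 7.2% to 9.0% all four exceed 99%. At the stronger HRs, power at 1.32% to 1.48% is at least 95% throughout; the lowest is rivaroxaban at HR 0.77.

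**5. Break-even.** The warfarin risk needed for 80% power at 6.33 years is events / N / [(1−p) + p × HR]: edoxaban 2.26%, rivaroxaban 1.33%, dabigatran 1.32%, apixaban 0.99%. The edoxaban value is above every risk the apixaban and dabigatran inputs imply at either HR; at the highest of those, 1.63%, edoxaban power is 66%.

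**6. Sensitivity case only.** The Abstract says all NOACs became available as first-line VTE treatment in May 2015. Suppose, as the plan does not state, that there was no earlier NOAC use for VTE. Dabigatran then accrues for 50 months: 866 × 50/12 = 3,608 users against 4,299 × 76/12 = 27,227 on warfarin (p = 0.117). At its own 1.4%, power is about 70%, or 73% if the patients projected to NOACs before that date are counted as warfarin users.

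**The case against.** The strongest reply is that the shortfall is conditional. It appears only if the low probabilities apply, and the cited sources may differ for good reasons. Table 2 is broad: many of its other-bleeding codes need only an admission, which could favour the higher risks. This stands, and it is why the finding is that power is not established rather than that the study is underpowered.

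Second, rivaroxaban falls below 80% at one corner only, by 0.4 points, and dabigatran never does outside the May 2015 case. At a warfarin risk of 1.63% they have about 87% and 88%. That also stands; borderline is the most that can be said of them.

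Third, Protocol 8 already plans power calculations in Phase I and makes Phase II depend on adequate power. The data are existing claims, so no recruitment target is set. This limits the harm. But that decision needs a coherent event risk, the plan offers four, and the closing sentences of each comparison carry no condition.

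Fourth, exact thresholds would suggest too much precision. They rest on 57 edoxaban and 26 dabigatran users (exact Poisson 95% limits about 43–74 and 17–38), a 3-month look-back instead of 12 months, and a formula that ignores precision lost to weighting. This is fair, and the thresholds should be presented as approximate.

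**Conclusion.** The point holds. The four event probabilities are mutually inconsistent for the planned outcome and comparator, and the accrual multiplier contradicts the entry window.

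The event probability does nearly all the work. The year count alone takes no comparison below 80%, and edoxaban at HR 0.81 misses 80% at the low risks even on the plan's own 7-year N. On the corrected N it would need roughly 1.5 to 1.7 times the projected patients (59,500/38,836 to 66,500/38,836), and the stated requirement of 9,703 would be too low by a factor of six to seven. Apixaban, and all comparisons at the stronger hazard ratios, are safe in every common-risk case above.

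These results assume that 2018 counts apply in every accrual year, that Schoenfeld's formula holds without a weighting penalty, and that one warfarin risk applies to all four comparisons.

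**What to change.** 1. Adopt one justified warfarin-arm major-bleeding risk for the Table 2 outcome, or one stated range, with its source. Derive each comparison's overall probability from it using that comparison's hazard ratio and allocation.
2. Replace 7 years with 76 months (6.33 years), giving projected totals of about 44,536 (apixaban), 80,636 (rivaroxaban), 38,836 (edoxaban) and 32,718 (dabigatran). State what is assumed about NOAC use before May 2015, with no earlier use as a sensitivity case only.
3. Make each power sentence conditional. For example: at the conservative hazard ratio and 6.33 accrual years, before any loss of precision from weighting, 80% power needs a warfarin-arm risk of at least about 2.27% (edoxaban), 1.34% (rivaroxaban), 1.32% (dabigatran) and 0.99% (apixaban).
4. Carry the same common inputs, updated with Phase I counts, into the Phase I power calculations already planned.

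The cost is text and recalculation in Protocol 9.5, the Abstract and SAP 9, with no extra patients or data. The power statement becomes less favourable, mainly for edoxaban.
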